IOTA5 interim analysis

Statistical Analysis Plan

Page 2-11: Follow-up study (27 December 2017)

Page 12-19: Performance of models for ovarian tumor diagnosis when applied to all patients (operated or conservatively followed) (28 May 2019)

IOTA5 interim analysis

Follow-up study

Statistical Analysis Plan

27 December 2017

1.1 Data:

The IOTA5 database will be used for the analysis and the following in- and exclusion criteria will be used.

Inclusion criteria:

- Initial policy is conservative management,
- The mass was diagnosed as benign at the first visit (i.e. subjective assessment = benign AND certainty = certainly benign OR probably benign).
- First scan between 1 January 2012 and 1 March 2015.

Exclusion criteria:

- Patients who did not give consent; data from patients who withdrew consent during the study will not be used either
- Younger than 18 years at first scan
- Cysts that are deemed clearly physiological and less than 3 cm in maximum diameter are not eligible for inclusion. [*We identified 13 such patients in the database for the interim analysis.*]

Further issues regarding data:

- Patients who underwent surgery for the adnexal mass after the first scan, despite the initial policy being conservative management, will be used in descriptive statistics but not in the main survival analysis. We will include them in a sensitivity analysis (cf below).
- Patients who withdrew consent during the study will not be used
- Only the dominant mass of the patient will be included
- We include follow-up data up to 30th of June 2017 such that all patients should have been followed up for 24 months (protocol allows +/- 2 months, hence this date allows 26 months follow-up for all patients; for the survival analysis, we use all available data (i.e. also information on the first scan after 26 months if available) but only show results up to 30 months. 30 months implies 2.5 years, this is convenient when constructing plots. Follow-up after 30 months is incomplete and hence results are uncertain.
- Although the aim of IOTA5 was to recruit patients consecutively and organize follow-up, there is a lot of heterogeneity among centers regarding adherence to the follow-up protocol. Therefore, we will perform a sensitivity analysis including all centers that have contributed to patient recruitment. However, only data of the following centers will be used for the primary analysis (centers with sufficient data quality: based on N recruited for conservative

management and % useful info): AGR, CIT, DEP, FLI, GBE, IUK, LBE, MIT, MPO, MSW, NCI, NUK, OIT, PSP, RIT, SIT, SSW, TIT and TUS.

1.2 Analysis:

1.2.1 Population

The population in this study consists of cases with a new adnexal mass (not already in follow-up in the center), and of patients with a mass that was already in follow-up in the center before the center started recruitment for the IOTA5 study. The latter group is likely a selected one: known masses that have spontaneously resolved or were operated on before the center started recruiting for the IOTA5 study will not be included. In addition, follow-up of these masses before the start of IOTA5 is ignored. Therefore, we assume that the patients with a known mass already in follow-up will more likely have a persistent and harmless mass. In this group, we can expect fewer spontaneous resolutions, less surgery for suspicion of malignancy or other complications, resulting in fewer confirmed complications. First, we will analyze the follow-up for all patients (new + known masses) in order to describe fully what was found during the IOTA5 study. Then, we will focus on follow-up results for patients with new masses only in order to obtain statistically more correct estimates.

Patients that have been selected for conservative management after subjective assessment by the ultrasound investigator, can nevertheless undergo surgery after inclusion, before having proceeded to follow-up (because of many reasons e.g. decision of the managing clinician, patient request etcetera). In the primary analysis we will describe this group with immediate surgery (why surgery was performed, what was found at surgery), but for the survival analysis only cases with at least one follow-up scan will be included (intention to treat with follow-up). In the appendix, we will add a sensitivity analysis that involves a survival analysis including patients with immediate surgery (intention to treat with or without follow-up).

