1.2.2 Methods

To describe findings during follow up, we will use cumulative incidence curves that reflect the competing risk setting. The follow-up time will be computed in months.

In competing risk survival analysis, the hazard and cumulative incidence of competing (i.e. mutually exclusive) events are estimated over time. The basic competing risk outcome levels reflect the overall study outcome, and are 'surgery performed', 'cyst spontaneously resolved', and 'patient died (for any reason)', whichever comes first. When surgery is performed, this can be further subdivided based on reason for surgery and findings at surgery. For these subdivisions, it is possible that two events (i.e. reasons or findings) occur simultaneously. For example, a patient can undergo surgery due to acute pain and fertility concerns. We therefore specified a hierarchy of the competing events and if two events occur simultaneously, the event highest in the hierarchy is given to the observation. The hierarchies are shown in Box 1. For example, when the patient is operated due to acute pain and fertility concerns, the patient is said to have the event acute pain.

Box 1. Hierarchy of reasons for surgery and findings at surgery.

Reasons for surgery	Findings at surgery
1. Suspicion of malignancy ^a	1. Invasive
2. Pain ^b	2. Borderline
3. Patient request/opportunistic ^c	3. Torsion
	4. Cyst rupture
	5. Minor complications ^d
	6. No complications of tumor

^a Includes ‘suspicion of malignancy based on ultrasound; suspicion of malignancy based on: increase in size, change in morphology, change in vascularity, raised or increase in CA125, raised HE4, CT finding, MRI findings’

^b Includes ‘acute pain (suspected torsion, suspected cyst rupture), chronic pain’

^c Includes ‘fertility concerns, patient request, opportunistic removal’

^d Includes ‘tumor bleeding, adhesions, inflammation/infection’

We will derive cumulative incidence functions for study outcome, reason for surgery, and findings at surgery. For each outcome, figures depicting the cumulative incidence will be produced, as well as tables at time points 12 and 24 months containing the cumulative incidences of the competing events with 95% CI.

Median follow-up will be estimated by the reverse Kaplan-Meier method, i.e. where censoring is denoted as the event, and events denoted as censoring. This is the common method to visualize the censoring function.

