Subgroup analyses will also be performed in the same manner as the overall analysis. Subgroup variables are tumour type (unilocular, unilocular-solid, multilocular, multilocular-solid, solid), presumed diagnosis (see table below), subjective assessment (certainly benign, probably benign), Lesion size (median split method + description on the cumulative incidence at cut-offs 3, 4, 5, 7, 10 cm), and menopausal status. For menopausal status, the data collection software contains a bug such that this information is overwritten by the menopausal status of the last visit. Therefore, for a small group of patients who are labeled postmenopausal, it is possible that they were premenopausal at the first visit in the study. However, we will use the variable as currently available in the dataset. If menopausal status is uncertain, we will classify it as postmenopausal if age at inclusion is 50 or higher.

In all subgroup analyses, we will report cumulative incidences on: spontaneous resolution, death (any cause), surgery (any reason), malignancy, torsion, rupture.

In the subgroup analyses, cumulative incidences will only be reported at 24 months.

Table. Presumed diagnoses at first visit

Presumed diagnosis	N (%)
Simple cyst / para-ovarian or salpingeal cyst/ Serous cystadenoma / serous cystadenofibroma	1470 (47%)
Endometrioma	609 (19%)
Teratoma	325 (10%)
Functional cyst	186 (6%)
Fibroma / fibrothecoma	180 (6%)
Mucinous cystadenoma / mucinous cystadenofibroma	129 (4%)
Hydrosalpinx	122 (4%)

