1.2.3 Planned analyses, figures, tables

This list does not indicate which figures or tables will be included in the main document.

Figure: Flowchart of patients

Table: Patient and tumor characteristics at inclusion for patients with initial policy conservative (including patients that were operated immediately). *The list of variables to be described can be augmented with other relevant variables according to clinicians, and these will be added irrespective of the results.*

	All patients	Patients with newly detected masses	Patients with masses already in follow-up
Age			
Menopausal status			
Time in follow-up before inclusion		NA	
Tumor type			
Lesion size			
Solid parts			
...			
Presumed diagnosis (endometrioma etc)			
...			
Subjective assessment (certainty)			
Immediately operated			
Patients with a newly detected masses, n (%)		NA	NA
Symptomatic at first scan			
Pain			
Abnormal bleeding			
Other symptoms			
Outcome events			
Cyst spontaneously resolved			
Surgery performed			
Invasive tumor			
Borderline tumor			
Cyst torsion			
Cyst rupture			
Complications detected at surgery*			
No complication detected at surgery			
Patient died			

Table: List of centers, with number of patients per center. This table will include all centers (all the ones included in the sensitivity analysis). Order by total number of patients (conservative and surgery). This table is intended to be included in the appendix or supplementary material.

Center	N	Initial policy surgery	Initial policy conservative	% No info	% Useful info
Malmo, Sweden					
Leuven, Belgium					
Rome, Italy					
...					
All oncology centers					
All non-oncology centers					
All centers					

Useful information: study outcome observed, or follow-up of at least 10 months.

Table: List of centers, with number of patients per center. This table will include centers with sufficient data quality (all the ones included in the primary analysis). Order by total number of patients (conservative). This table is intended to be included in the main report.

Center	Initial policy conservative	% Useful info
Malmo, Sweden		
Leuven, Belgium		
Rome, Italy		
...		
All oncology centers		
All non-oncology centers		
All centers		

Figure: Histogram of time of follow-up before recruitment in IOTA5 for patients with a mass already in follow-up at inclusion ('old' patients)

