Figure: Histogram of time of follow up scans (all follow up scans, i.e. not only the last scan per patient). This will be done once based on data from all patients, and once based on data from patients with newly detected masses only.

Figure: Cumulative incidence curve for study outcome (died, resolution, surgery). This will be done once based on data from all patients, and once based on data from patients with newly detected masses only.

Figure: Cumulative incidence curves for reason for surgery (study outcome surgery is subdivided into different reasons as specified above in Box 1; only curves for these reasons are given, not for other study outcomes (died/resolved)). This will be done once based on data from all patients, and once based on data from patients with newly detected masses only.

Figure: Cumulative incidence curves for surgery outcome (study outcome is again subdivided, but now in terms of findings at surgery as specified above in Box 1). Panel A gives all events with y-axis from 0 to 1; Panel B given zoomed in plot focusing only on malignancy, torsion, rupture. This will be done once based on data from all patients, and once based on data from patients with newly detected masses only.

Table: Cumulative incidence of study outcomes, reasons for surgery, and findings at surgery at 12 and 24 months with 95% CI; Table containing the following statistics at time points 12 months and 24 months: cumulative incidence with standard error and 95% CI. This will be done once based on data from all patients, and once based on data from patients with newly detected masses only.

	12 months	24 months
Study outcome		
Cyst resolution		
Patient died		
Surgery performed		
Reason for surgery		
Suspicion of malignancy		
Pain ^b		
Patient request/opportunistic ^c		
Findings at surgery		
Invasive		
Borderline		
Torsion		
Cyst rupture		
Minor complications		
No complications		

Table: Table of all cases with confirmed malignancy, rupture, or torsion, with descriptive information. *The exact list of parameters to be described should still be defined.*

Case	New or known mass at inclusion	Time in follow up before surgery	Finding(s) at surgery	Age at inclusion	Lesion size at first scan	Change in lesion size	...
1							
2							
3							
4							
5							
6							
7							
...							

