Table: Cumulative incidence of each outcome (death (any cause), spontaneous resolution, surgery (any reason), malignancy, torsion, rupture at 24 months with 95% CI for all levels of all subgroup variables for patients with new masses. This will be done based on data from patients with newly detected masses only.

Subgroup variable	Death (any cause)	Spontaneous resolution	Surgery (any reason)	Malignancy	Torsion	Rupture
Tumor type						
Unilocular						
Unilocular-solid						
...						
Presumed diagnosis						
Endometriosis						
...						
Subjective assessment						
Certainly benign						
Probably benign						
...						
Lesion size						
median split (4 cm?)						
cut-offs 3, 4, 5, 7, 10 cm						
...						
Menopausal status						
Premenopausal						
Postmenopausal						

Table: For cases with initial policy conservative but who were nevertheless immediately operated: overview of histology at surgery. This will be done based on data from patients with newly detected masses only.

Histology	N (%)
Endometrioma	
Dermoid	
...	
Borderline	
...	

Table: Overview of reasons for surgery for cases with initial policy conservative, stratified by whether they were nevertheless immediately operated or not. This will be done based on data from patients with newly detected masses only.

Reason for surgery	Immediately operated N (%)	Patients with FU N (%)
Suspicion of malignancy		
Pain		
Suspected torsion		
Suspected cyst rupture		
Acute pain		
Chronic pain		
Patient request / opportunistic		
Fertility concerns		
Patient request, other		
Opportunistic		

Table. Sensitivity analysis using data from all centres. This will be done based on data from patients with newly detected masses only.

	12 months	24 months
Study outcome		
Cyst resolution		
Patient died		
Surgery performed		
Reason for surgery		
Suspicion of malignancy		
Pain ^b		
Patient request/opportunistic ^c		
Findings at surgery		
Invasive		
Borderline		
Torsion		
Cyst rupture		
Minor complications		
No complications		

Table. Sensitivity analysis including patients that were immediately operated. This will be done based on data from patients with newly detected masses only.

	12 months	24 months
Study outcome		
Cyst resolution		
Patient died		
Surgery performed		
Reason for surgery		
Suspicion of malignancy		
Pain ^b		
Patient request/opportunistic ^c		
Findings at surgery		
Invasive		
Borderline		
Torsion		
Cyst rupture		
Minor complications		
No complications		

IOTA5 interim analysis

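### The 24-month subgroup table for new masses counts only patients who reached a follow-up scan, with no version that includes earlier surgery

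*SAP*

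**What the plan says.** The follow-up SAP (27 December 2017) sets the rule twice. Section 1.1, under further data issues, says that patients operated after the first scan despite a conservative initial policy "will be used in descriptive statistics but not in the main survival analysis". Section 1.2.1 says that "for the survival analysis only cases with at least one follow-up scan will be included (intention to treat with follow-up". The Protocol (Follow-up) places the first follow-up scan at 3 months, with a range of 1-4 months.

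On time, section 1.2.2 says only "The follow-up time will be computed in months". No origin, landmark or delayed entry is given. Section 1.1 counts the 24 months of follow-up from the recruitment scan, and section 1.2.1 ignores follow-up before enrolment. Both imply that time zero is the inclusion scan.

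The SAP discloses the excluded group and describes it:

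- Section 1.2.1: "In the appendix, we will add a sensitivity analysis that involves a survival analysis including patients with immediate surgery".
- Section 1.2.3: "Table. Sensitivity analysis including patients that were immediately operated. This will be done based on data from patients with newly detected masses only". This table has 12- and 24-month columns, with rows for study outcome, reason for surgery and findings at surgery, but none for subgroups.
- Section 1.2.3 also plans a table of "Patient and tumor characteristics at inclusion for patients with initial policy conservative (including patients that were operated immediately", with an immediate-surgery row and outcome counts for all, new and known masses.
- For new masses, immediate operations are tabulated by histology and by reason for surgery.
- There is also a "Table of all cases with confirmed malignancy, rupture, or torsion, with descriptive information".

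For subgroups, section 1.2.2 says "Subgroup analyses will also be performed in the same manner as the overall analysis". The resulting table reports 24-month incidences for new masses, by tumour type, presumed diagnosis, certainty of the subjective assessment, lesion size and menopausal status.

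**The concern.** Surgery is one of the three competing outcomes. A woman chosen for conservative management but operated before her first follow-up scan leaves the main analysis instead of counting as an event. With time zero at inclusion, each patient's interval before her first scan is free of surgery and death by construction. The curves answer a question about women who got as far as a scan, not about women for whom conservative management was chosen.

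For new masses overall, the planned sensitivity table lets a reader see the difference. For subgroups nothing does. If immediate surgery is more common in, say, larger or more complex masses, the scanned-only table removes more events from those levels than from others. A real difference in surgery could then look smaller, disappear or change sign. Histology at surgery is not presumed diagnosis, tumour type or lesion size at the first visit, so the planned immediate-surgery tables do not let a reader repair the subgroup rows.

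**Working it through.** **Inputs.** The documents give no sample-size figure to reproduce and no count of early operations. Every s, d, F and R below is an assumption: s and d are the shares with surgery and death before the first scan among patients with any information after inclusion, F is the 24-month surgery incidence among scanned patients, and R is their incidence of resolution.

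**Formula.** The inclusive incidence is s + (1 - s - d)F. The shortfall of the scanned-only figure is therefore s(1 - F) - dF. With d = 0, in percentage points:

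| s | F = 10% | F = 15% | F = 20% |
|---|---|---|---|
| 1% | 0.90 | 0.85 | 0.80 |
| 2% | 1.8 | 1.7 | 1.6 |
| 5% | 4.5 | 4.25 | 4.0 |
| 10% | 9.0 | 8.5 | 8.0 |

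Taking d = 0.2% lowers these by dF, only 0.02-0.04 points. Resolution moves the other way, because the inclusive figure is (1 - s)R. With R = 20% it becomes 19.8, 19.6, 19.0 and 18.0% for the four values of s.

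**Check by simulation.** The simulation had 60,000 patients, first scan uniform on 1-4 months, resolution seen only at scans, and time from inclusion. The assumed monthly surgery hazard was 0.005-0.03 up to 3 months and 0.005 after. Between 1.3% and 6.7% of patients were dropped. Aalen-Johansen surgery incidence at 24 months was 9.2% scanned-only against 10.4% inclusive at the low end, and 11.0% against 17.0% at the high end. The formula gives 0.013 + 0.987 x 0.092 = 10.4% and 0.067 + 0.933 x 0.110 = 17.0%.

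**Scale.** The counts and rounded percentages in the presumed-diagnosis table (section 1.2.2) are mutually consistent for a total of 3,123-3,161 patients; the table does not state its population. At N = 3,140, the shortfall equals the binomial 95% half-width when s = 1.96 x sqrt(F/((1 - F)N)). That is 1.2% for F = 10% and 1.7% for F = 20%, or 37 to 55 patients. If 1,500-2,000 are new masses (assumed), the range is 1.5-2.5%.

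**Subgroups.** Let F = 15% in two levels, with s = 1% in one and 5% in the other:

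- Scanned-only: 15% against 15%, no difference.
- Inclusive: 0.01 + 0.99 x 0.15 = 15.85%, and 0.05 + 0.95 x 0.15 = 19.25%. The hidden difference is 3.4 points.

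For comparison, a median split of 1,500-2,000 new masses gives 750-1,000 per level. The 95% half-width of a difference at 15% is 1.96 x sqrt(2 x 0.15 x 0.85/n), which is 3.6 points at n = 750 and 3.1 at n = 1,000. The hidden difference would be about as large as the sampling error.

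**Single findings.** For finding k the shortfall is s_k - (s + d)F_k, which can take either sign. Assume F_k = 0.6% and 63 pre-scan exits out of 3,140 (2%). With no such case among them, the scanned-only figure is 0.012 points too high. With one case it is 1/3,140 - 0.012% = 0.020 too low, and with three cases 0.084 too low.

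**The case against.** The strongest reply is that this is a disclosed choice of estimand. Section 1.2.2 says that the curves describe findings during follow-up. Section 1.2.1 names both populations, makes one primary, and explains that immediate surgery includes clinician decisions and patient requests. The inclusive table is planned for new masses, which the SAP regards as giving the more correct estimates. For the all-patient population, a reader can approximate the correction by putting the immediate-surgery row and the scanned-only incidence into the formula above. The early-death gap is negligible: at d = 0.2%, an inclusive table that omits early deaths overstates surgery by 0.02-0.06 points. Whether that table sits in the appendix or the main text is a matter of presentation. All of this stands.

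It does not reach the subgroup table. That table belongs to the preferred new-mass population, and it has neither an inclusive version nor immediate-surgery counts by level.

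Stronger readings are tempting, but the documents do not support them:

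- A reader might infer that malignancy, torsion and rupture are understated. That holds only if their share of pre-scan exits exceeds their incidence among scanned patients. The listing of confirmed cases is planned as well.
- A reader might infer that surgery is understated among everyone selected. Patients with no information after inclusion matter here. If they are assumed event-free, the direction reverses once their share exceeds 5.4% (0.85/15.85, at s = 1% and F = 15%).
- A reader might take the remark in section 1.5.1 of the May 2019 SAP as evidence that such patients are a large group here. It ranks groups among uncertain-outcome cases in a different analysis population.

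**Conclusion.** The point holds as a cheap improvement. It is certain that the main survival analysis conditions on reaching a follow-up scan and that no time origin is stated. With time from inclusion, surgery is understated relative to all conservatively selected patients with information after inclusion, by about s(1 - F). The amount cannot be known from the documents, so the sizes above are illustrative and rest on assumed s and F.

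For new masses overall, the planned sensitivity table already deals with this. The gap that matters is the 24-month subgroup table: it inherits the restriction, and a reader cannot tell whether pre-scan surgery differs between levels. The missing inclusive analysis for the all-patient population is a lesser gap.

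**What to change.** 1. State in section 1.2.2 that time zero is the inclusion scan.
2. Label the scanned-only curves and tables as conditional on reaching a follow-up scan.
3. Rerun the 24-month subgroup table for new masses with immediate surgeries counted as events. Set it beside the scanned-only version, with the number of immediate surgeries in each level.
4. At little extra work, produce the same inclusive 12- and 24-month table for the all-patient population. Count any deaths before the first scan as events in the inclusive analyses.

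The scanned-only analysis can stay primary, and the overall inclusive tables can stay in the appendix. Delayed entry alone would not do, because it cannot restore surgery before the first scan.

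The cost is a few sentences of SAP text and a rerun of planned analyses on data already held. The downside is some extra table columns and a surgery incidence that includes elective changes of plan. The reason-for-surgery rows in the overall tables make those visible.
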